#### **8.1.2. Sensitivity Analyses of the Co-Primary Endpoints**

Besides the scenario with the observed missing data for the co-primary efficacy endpoints, two additional scenarios will be considered for each of the co-primary endpoints.

For the first co-primary endpoint, in one scenario, subjects with missing headache pain assessments at 2 hours postdose will be assigned as having a pain level of 3 (severe) at 2 hours postdose; that is, they will be assigned as having severe headache pain at 2 hours postdose. In another scenario, subjects with missing headache pain assessments at 2 hours postdose will be assigned as having a pain level of 0 (None) at 2 hours postdose; that is, they will be assigned as having headache pain freedom at 2 hours postdose.

For the second co-primary endpoint, in one scenario, subjects with a missing response for MBS status will be assigned as being free from their MBS. In another scenario, subjects with a missing response for MBS status will be assigned as not being free from their MBS.

For the first co-primary endpoint, proportions of subjects pain-free at 2 hours postdose for the DFN-15 and placebo groups, 95% exact CIs for those proportions, and the corresponding p-value from Fisher's exact test for the three scenarios will be presented. A similar analysis will be conducted for the proportion of subjects who are free from their MBS at 2 hours postdose.

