#### Full Analysis Set

Each DB treatment period will have a full analysis set (FAS), which will include all randomized subjects who during the treatment period took at least one dose of study drug and have at least

1 post-baseline efficacy assessment for either pain or symptom (among nausea, photophobia, phonophobia). Subjects in DB1 will be analyzed according to their randomized treatment. Subjects in DB2 will be analyzed according to their re-randomized treatment. The FAS will be used for all analyses of efficacy endpoints.

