### 5.3. SAFETY SET

The Safety Set (SS) will include all subjects who took at least one dose of DB study drug during one or both treatment periods, and have it recorded in their eDiary. Subjects will be analyzed according to the treatment they receive. The Safety Set 1 (SS1) will include randomized subjects who took at least one dose of DB study drug during the DB1 treatment period. The Safety Set 2 (SS2) will include subjects who were re-randomized and took at least one dose of DB study drug during the DB2 treatment period. The SS, SS1, and SS2 will be used for all analyses of safety endpoints including summaries of TEAEs, ECGs, and clinical laboratory results.

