### 5.4. FULL ANALYSIS SET

Each DB treatment period will have a Full Analysis Set (FAS). The Full Analysis Set 1 (FAS1) will include all randomized subjects who took at least one dose of study drug during the DB1 treatment period and have at least one post-baseline efficacy time point assessment for either pain or symptom (among nausea, photophobia, phonophobia) in DB1. The Full Analysis Set 2 (FAS2) will include all re-randomized subjects who took at least one dose of study drug during the DB2 treatment period and have at least one post-baseline efficacy time point assessment for either pain or symptom (among nausea, photophobia, phonophobia). Subjects in the DB1 will be analyzed according to their randomized treatment. Subjects in the DB2 will be analyzed according to their re-randomized treatment. The FAS1 and FAS2 will be used for all analyses of efficacy endpoints.

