### 5.5. PER PROTOCOL SET

The Per Protocol Set (PPS) will include all FAS1 subjects who have at least 1 post-baseline primary endpoint assessment for both co-primary endpoints (observed and LOCF), and who have no significant protocol deviations that will impact the collection

or interpretation of the co-primary endpoint data during the DB1 treatment period. Identification of subjects in the PPS will be determined before the database lock and unblinding. Subjects in the PPS will be analyzed according to their DB1 randomized treatment.

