The number of subjects with response, the number of subjects with non-missing assessment, proportions for the DFN-15 and placebo groups, 95% exact CIs for those proportions, the odds ratio for response, and the corresponding p-value will be presented for the comparison between two treatment groups for the FAS1. This analysis will exclude subjects who took rescue medication prior to the data collection of the 2 hours postdose time point (inclusive; LOCF), as well as subjects who have predose pain level = mild (Grade 1) or none (Grade 0). The analysis will also be performed using the PPS.

If the first co-primary efficacy endpoint is statistically significant, results will be found similarly for the second co-primary efficacy endpoint.

If statistical significance ( $p < 0.05$ ) is not achieved for either study 006 or study 007 (or both studies) co-primary endpoints, additional analyses will be conducted. Detailed information will be included in a separated Statistical Analysis Plan.

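### The missing-data scenarios in SAP 8.1.2 fall by default on FAS1, so they cover partly missing diaries but not dosed DB1 subjects with no postdose pain or symptom entry

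*SAP*

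**What the plan says.** SAP 8.1.2 adds two scenarios per co-primary endpoint to the observed-data result. For pain, a missing 2-hour value is set to severe in one scenario ("subjects with missing headache pain assessments at 2 hours postdose will be assigned as having a pain level of 3 (severe") and to none in the other. For the Screening MBS, a missing status is set to free in one, and in the other "subjects with a missing response for MBS status will be assigned as not being free from their MBS". No analysis set is named there.

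SAP 5.4 supplies one through its general rule: "The FAS1 and FAS2 will be used for all analyses of efficacy endpoints". To be in FAS1, a subject must have taken DB1 study drug and must "have at least one post-baseline efficacy time point assessment for either pain or symptom (among nausea, photophobia, phonophobia) in DB1". Protocol 10.2 has the same condition ("1 post-baseline efficacy assessment for either pain or symptom (among nausea, photophobia, phonophobia").

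The other co-primary results do not reach further. The primary results in SAP 8.1.1 "will be presented for the comparison between two treatment groups for the FAS1", and the per-protocol set is drawn from within FAS1: "The Per Protocol Set (PPS) will include all FAS1 subjects who have at least 1 post-baseline primary endpoint assessment for both co-primary endpoints". SS1 has no postdose-entry condition (it "will include randomized subjects who took at least one dose of DB study drug during the DB1 treatment period"), but SAP 5.3 assigns it to safety.

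**The concern.** A randomized subject who takes the DB1 dose and then records no pain or symptom has a missing 2-hour outcome by definition. That subject is removed before 8.1.2 assigns any value, and is also absent from the LOCF, observed-data and per-protocol results. All four scenarios share the gap.

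Making an entry happens after randomization and dosing, so selecting on it is selection on a post-treatment event. Best-case and worst-case scenarios are meant to show how far missing data could move the result. These show it only for subjects who left some data. Someone reading the severe-pain scenario would reasonably assume that every dosed subject with no 2-hour value was counted as a failure.

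**Working it through.** **Which set applies.** SAP 8.1.2 is silent; 5.4 covers all efficacy analyses; 8.1.1 reports on FAS1. The scenarios therefore run on FAS1. This is an inference from 5.4, not a statement in 8.1.2.

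**Who is lost.** SAP Table 2 schedules pain and symptoms at 15, 30 and 45 minutes and at 1, 1.5, 2, 4 and 24 hours. One entry at any of these eight times keeps the subject in FAS1, and missing 2-hour pain is then set to severe. Only a diary with no pain or symptom entry at all eight times is lost.

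**The plan's own figure.** Inputs from Protocol 10.7 and SAP 3.5: 17.6% versus 29.2% pain-free, 600 randomized 1:1, two-sided 5%, 15% dropout, stated power 88%.
- n per arm = 600 × 0.85 / 2 = 255
- z = [|p2 − p1|√n − 1.96√(2p̄(1 − p̄))] / √(p1(1 − p1) + p2(1 − p2)), with p̄ = 0.234
- z = (1.852 − 1.174) / 0.593 = 1.14, so power is 87.4%. With 600 / 1.15 / 2 = 261 per arm it is 88.1%.

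The stated 88% reproduces and is not in dispute. I use 255 per arm only as a plausible size for FAS1.

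**Effect of adding the omitted subjects as failures.** The documents give no count, so the numbers added are assumptions. For each pair (a added on DFN-15, b added on placebo), I ran a two-sided Fisher's exact test on x/(255 + a) versus 45/(255 + b). Here 45/255 = 17.6%. The borderline case is x = 65 (25.5%), the smallest count that is significant against 45. The planned case is x = 74 (29.0%).

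| Added: DFN-15, placebo | p, 65 vs 45 | p, 74 vs 45 |
|---|---|---|
| 0, 0 | 0.040 | 0.0033 |
| 5, 5 | 0.041 | 0.0034 |
| 13, 13 | 0.042 | 0.0035 |
| 4, 0 | 0.042 | 0.0035 |
| 5, 0 | 0.053 | 0.0046 |
| 8, 2 | 0.053 | 0.0047 |
| 13, 3 | 0.068 | 0.0066 |
| 0, 5 | 0.024 | 0.0017 |
| 2, 8 | 0.024 | 0.0017 |
| 3, 13 | 0.019 | 0.0012 |

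The move from 0.042 to 0.053 between the fourth and fifth DFN-15 subject is a step caused by the discreteness of Fisher's test, not a steep trend. In the planned case, 45 added on DFN-15 and none on placebo still give p=0.049.

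**Second co-primary endpoint.** Protocol 10.7 gives 480 subjects with 15% dropout, so 480 × 0.85 / 2 = 204 per arm. A borderline 78/204 versus 58/204 gives p=0.046. Four failures added on DFN-15 only give 0.059, four in each arm give 0.047, and four on placebo only give 0.028. The pattern is the same.

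**The case against.** The case on the other side is substantial.

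- **The group is narrow.** A reader might infer that the severe-pain scenario misses everyone who vomited, felt too ill or gave up on the diary. It does not: anyone with a single postdose pain or symptom entry is counted as a failure if 2-hour pain is missing. The documents give no reasons for blank diaries, so linking them to illness would be conjecture. This stands.
- **The direction is unknown.** A reader might infer that the omission favours DFN-15. The table shows that an excess of blank diaries on placebo lowers the p-value, so leaving those subjects out would be conservative. The trial is blinded with matching placebo. Exclusion also requires no entry at 15 minutes, against a median time to peak of 0.67 h for the 50 mg/mL solution (Protocol 8.2). That weakens the case for treatment-driven non-entry at the earliest times without excluding it. This also stands.
- **The count is mostly visible already.** SAP 7.1 reports numbers in SS1 and FAS1, and SAP 6.1.2 presents summaries by treatment unless otherwise specified. Apart from any subject given the wrong kit, SS1 minus FAS1 is the number in question. This largely stands, but 7.1 does not expressly promise the count by arm, and no planned test includes these subjects.
- **A full analysis set with a postdose-entry condition is prespecified alike in both documents.** True, and the point leaves it in place for the primary analysis. It does not follow that the sensitivity analysis should share the same omission.

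**Conclusion.** The gap is real and modest. On the text, a dosed DB1 subject with no postdose pain or symptom entry is in no co-primary analysis, including the scenarios meant to bound missing 2-hour data. The result would change only if three things held together: a borderline result, enough blank diaries, and an imbalance between arms. With balanced numbers p hardly moves (0.040 to 0.042 with 13 added per arm), and at about the planned effect none of the tabulated cases overturns significance. All of this rests on assumed counts, on 255 per arm (204 for the second endpoint), and on 5.4 governing 8.1.2. If 5.4 does not govern, the set for 8.1.2 is unspecified and still has to be named.

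A reader might go further and conclude that the primary analysis is invalid, that type I error is inflated, or that a positive result would be falsely robust. The documents support none of these. They show only that the scenarios have a narrower reach than their wording suggests.

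**What to change.** - In SAP 8.1.2, state that both scenarios, for both co-primary endpoints, use all randomized subjects with a DB1 dose recorded in the eDiary, analysed as randomized, with predose pain of Grade 2 or 3 and, for the second endpoint, the Screening MBS present predose. Impose no postdose-entry requirement.
- Add a matching exception to the general rule in SAP 5.4.
- State whether the 8.1.1 analysis exclusion for rescue taken up to the 2-hour time point also applies to these scenarios. At present 8.1.2 does not say, and widening the set without settling this would change two things at once.
- Keep FAS1 for the primary analysis.
- In the 7.1 disposition table, show SS1 minus FAS1 by randomized arm.

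The cost is a few sentences in two sections, one disposition row and a rerun of tables already planned. The failure scenario may come out slightly less favourable. Subjects with no predose diary data remain uncounted, because their eligibility for the analysis cannot be established.

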#### **8.1.3. Supplemental Analyses of the Absence of Screening MBS**

Supplemental analysis will be conducted for the proportion of subjects who are free from their Screening MBS at 2 hours postdose with break down by individual symptoms (nausea, photophobia, and phonophobia) compared between DFN-15 and placebo in the DB1 treatment period.

### **8.2. SECONDARY ENDPOINTS AND ANALYSES**

The secondary endpoints that involve proportions of subjects who have a response will be summarized by treatment group and will be analyzed using the LOCF for missing secondary efficacy endpoint data.

Secondary endpoint analyses will be conducted as indicated for the FAS1 and FAS2 and will exclude subjects who took rescue medication prior to the data collection of the 2

hours postdose time point (inclusive; LOCF). For all secondary endpoint analyses in DB1 for the FAS1, subjects who have predose pain level = mild (Grade 1) or none (Grade 0) will also be excluded. For all secondary endpoint analyses in DB2 for the FAS2, subjects who have predose pain level = none (Grade 0) will also be excluded.

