#### **8.2.2. Freedom from Nausea, Photophobia, and Phonophobia Postdose**

The proportion of subjects who are free from nausea, photophobia, and phonophobia at 15, 30, and 45 minutes and 1, 1.5, 2, 4, and 24 hours postdose during each DB treatment period will be summarized by symptom, treatment group, and time point for the FAS1 and FAS2. The corresponding p-values from Fisher's exact test will be computed for the comparison between treatment groups. Subjects who report a symptom predose and report the status of the symptom at the particular postdose time point will be analyzed.

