#### **8.2.4. Headache Pain Relief Postdose**

The proportion of subjects who have pain relief at 15, 30, and 45 minutes and 1, 1.5, 2, 4, and 24 hours postdose will be summarized by treatment group and time point for the FAS1 and FAS2. For DB1, headache pain relief is defined as a reduction in migraine pain from predose severe or moderate to mild or none postdose. For DB2, headache pain relief is defined as moderate or severe pain predose reduced to mild or none postdose, or mild pain predose reduced to none postdose. The corresponding p-values from Fisher's exact test will be computed for the comparison between treatment groups. Subjects who report a headache predose and rate the headache pain level at the particular postdose time point will be analyzed.

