#### **8.2.5. Headache Pain Freedom Postdose**

The proportion of subjects who are pain-free at 15, 30, and 45 minutes and 1, 1.5, 2 (DB2 period), 4, and 24 hours postdose during each DB treatment period will be summarized by treatment group for the FAS1 and FAS2. The corresponding p-values from Fisher's exact test will be computed for the comparison between treatment groups.

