#### **8.2.10. Headache Pain Recurrence Postdose**

The proportion of subjects who have pain recurrence between 2 to 24 hours postdose during each DB treatment period will be summarized by treatment group for the FAS1 and FAS2. Pain recurrence between 2 to 24 hours is defined as pain-free at 2 hours postdose, with pain (mild, moderate, or severe) reported at 24 hours postdose. The corresponding p-values from Fisher's exact test will be computed for the comparison between treatment groups.

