#### **8.2.12. Sustained Headache Pain Freedom Postdose**

The proportion of subjects who have sustained pain freedom at 2 to 24 hours postdose during each DB treatment period will be summarized by treatment group for the FAS1 and FAS2. Sustained pain freedom at 2 to 24 hours is defined as pain-free at 2 hours postdose, with no use of rescue medication and no recurrence of headache pain within 2 to 24 hours postdose. The corresponding p-values from Fisher's exact test will be computed for the comparison between treatment groups.

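### Carrying the last pain rating forward to 24 hours lets a missing diary entry count as sustained pain freedom or relief and as no recurrence

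*SAP*

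**What the plan says.** SAP section 8.2 sets one imputation rule for secondary endpoints that are proportions of responders: they "will be analyzed using the LOCF for missing secondary efficacy endpoint data". Three of these endpoints ask what happened between 2 and 24 hours.

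- **Recurrence (8.2.10):** "pain-free at 2 hours postdose, with pain (mild, moderate, or severe) reported at 24 hours postdose".
- **Sustained pain relief (8.2.11):** relief at 2 hours, then no rescue and no worsening up to 24 hours.
- **Sustained pain freedom (8.2.12):** pain-free at 2 hours, "with no use of rescue medication and no recurrence of headache pain within 2 to 24 hours postdose".

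None of the three says what to do when the 24-hour rating is missing. After 2 hours, pain is rated only at 4 and 24 hours (SAP Table 2). Each endpoint gets a Fisher exact p-value.

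Other parts of the SAP point to observed cases. Section 6.3 bases analyses on non-missing values. Section 8.2.2 limits symptom freedom to subjects who "report the status of the symptom at the particular postdose time point will be analyzed", and 8.2.4 limits pain relief to those who "rate the headache pain level at the particular postdose time point will be analyzed". Section 8.2.6 does the same for absence of the most bothersome symptom. That restriction does not appear in 8.2.10 to 8.2.12.

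The separate display of observed data (8.1.1) and the best-case and worst-case scenarios (8.1.2) are stated for the co-primary endpoints only.

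**The concern.** These endpoints measure whether a 2-hour response lasts. Carrying a 2- or 4-hour value to 24 hours assumes that it did. The subjects exposed to this assumption are the 2-hour responders, and the plan expects more of them on DFN-15 (29.2% against 17.6%). The same share of missing diaries therefore adds more unearned successes to the active arm. Protocol section 10 foresees hypothesis tests for all secondary efficacy endpoints, so these results may be reported with p-values as evidence of durability.

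**Working it through.** **Inputs from the documents.** The 2-hour pain-free rates are 29.2% on DFN-15 and 17.6% on placebo, a gap of 11.6 points. The plan has 600 subjects, 1:1 allocation, 15% dropout and two-sided 5% (Protocol 10.7, SAP 3.5 and 3.6). That leaves 600 × 0.85 / 2 = 255 per arm.

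**The plan's own figure.** With 255 per arm, the normal-approximation power for 17.6% against 29.2% is 87.4%; with 600 / 1.15 / 2 ≈ 260 per arm it is 88.0%. The stated 88% reproduces. The documents give no figure for the sustained or recurrence endpoints.

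**Assumptions, none of them in the documents.**
- r: recurrence by 24 hours among 2-hour pain-free subjects
- m: share of those subjects with no 24-hour rating
- c: share of recurrences among the missing that still show up, through pain at 4 hours or recorded rescue

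**Formulas for one arm with 2-hour rate p.**
- True sustained rate: p(1 − r)
- Under LOCF: p[1 − r(1 − m) − r·m·c]
- Missing scored as not sustained: p(1 − m)(1 − r)

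LOCF exceeds the truth by p·m·r·(1 − c) in each arm. With equal r, m and c, the difference is inflated by m·r·(1 − c) × 11.6 points.

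| r | m | c | True difference | LOCF | Missing = not sustained |
|---|---|---|---|---|---|
| 20% | 5% | 0 | 9.28 | 9.40 | 8.82 |
| 30% | 10% | 0 | 8.12 | 8.47 | 7.31 |
| 30% | 10% | 0.6 | 8.12 | 8.26 | 7.31 |
| 40% | 20% | 0 | 6.96 | 7.89 | 5.57 |
| 50% | 10% | 0 | 5.80 | 6.38 | 5.22 |
| 50% | 20% | 0 | 5.80 | 6.96 | 4.64 |

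For r of 20 to 40%, m of 5 to 20% and c = 0, the inflation is 0.1 to 0.9 points. At r = 50% it is 0.6 points (m = 10%) and 1.2 points (m = 20%).

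**No sustained advantage.** Let both arms have the same true sustained rate S. With c = 0 the LOCF rate is S(1 − m) + p·m, so the spurious difference is m × 11.6 points. Take S = 12% (assumed) and 255 per arm.

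| m, both arms | LOCF rates | Difference | Exact chance of a Fisher result favouring DFN-15 |
|---|---|---|---|
| 0 | 12.0% vs 12.0% | 0 | 1.8% |
| 10% | 13.7% vs 12.6% | 1.2 | 4.4% |
| 20% | 15.4% vs 13.1% | 2.3 | 9.1% |

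The nominal one-directional limit is 2.5%. Scoring missing as not sustained keeps the chance at 1.8% when missingness is equal.

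**Unequal missingness (r = 50%, c = 0, true difference 5.8).**
- 20% missing on DFN-15, 10% on placebo: LOCF gives 17.5% − 9.7% = 7.8 points. Missing as not sustained gives 11.7% − 7.9% = 3.8.
- 10% missing on DFN-15, 20% on placebo: LOCF gives 16.1% − 10.6% = 5.5 points, below the truth.

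**Recurrence over the full analysis set (r = 30%, m = 10%, c = 0).** The true rates are 8.76% against 5.28%, a difference of 3.48 points. LOCF gives 7.88% against 4.75%, a difference of 3.13. The gap is an excess on DFN-15, which has more responders at risk, so narrowing it also favours the drug.

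**The case against.** A reader might infer that every 2-hour responder without a 24-hour diary is automatically scored as sustained and can never be a recurrence. The documents do not support that. Pain at 4 hours would be the value carried, and rescue from 2 to 24 hours defeats both sustained endpoints. SAP 9.2 allows rescue to be reported outside the eDiary, and medications are reviewed at Visits 3 and 4, so c may be well above zero. It remains unsettled whether a carried 4-hour pain value counts as recurrence, because 8.2.10 asks for pain "with pain (mild, moderate, or severe) reported at 24 hours postdose".

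A reader might also infer that LOCF always inflates the difference. It does not. With c = 0 the difference shrinks when the product of missingness and recurrence on placebo exceeds 0.292 / 0.176 = 1.66 times that on DFN-15. For example, with r = 30% and 5% against 20% missing, the difference falls from 8.12 to 7.50. With equal r, m and c, the ratio of the two sustained rates is unchanged.

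Nor does LOCF clearly govern every secondary proportion, given 6.3, 8.2.2, 8.2.4 and 8.2.6.

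The alternative rule has its own error. Per arm with c = 0, LOCF errs by +p·m·r and missing-as-not-sustained by −p·m·(1 − r), so the latter errs more whenever fewer than half of responders relapse. Finally, SAP 6.1.1 says only that secondary tests can be performed, and the SAP sets no confirmatory hierarchy for them.

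All of this stands, and it limits the size and certainty of the bias. It does not remove the fault: the only imputation rule that reaches these endpoints can supply the outcome they are meant to observe, with no sensitivity analysis to show how much.

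**Conclusion.** The point holds in a limited form. As written, the SAP scores a 2-hour pain-free subject with no 24-hour rating as sustained and not recurrent when no rescue is recorded and the 4-hour rating is pain-free or missing. Sustained rates are overstated and recurrence understated in each arm.

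With equal missingness and recurrence, the effect on the sustained pain-free difference is modest, and smaller still if 4-hour ratings and rescue records catch some recurrences. It matters most when the drug raises 2-hour response without a lasting benefit. That case is demanding: S = 12% in both arms implies that 12 / 29.2 = 41% of DFN-15 responders and 12 / 17.6 = 68% of placebo responders stay pain-free. Missingness, recurrence and c are assumptions throughout. No size is given for sustained relief, because the documents state no 2-hour relief rate. The direction of bias in the difference is not guaranteed. Trial success rests on the 2-hour co-primary endpoints and is unaffected.

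**What to change.** 1. In SAP 8.2.10 to 8.2.12, state that no 2- or 4-hour value is carried forward to 24 hours.
2. For sustained relief and sustained freedom, score a missing 24-hour rating as not sustained, and show an observed-case analysis beside it.
3. Analyse recurrence in subjects with an observed 24-hour rating.
4. Reconcile the LOCF sentence in 8.2 with 6.3, 8.2.2, 8.2.4 and 8.2.6.

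The cost is a sentence or two in 8.2.10 to 8.2.12, matching edits to the conflicting sections, and additional observed-case results for the sustained endpoints. The statistical price is conservatism. Both sustained rates fall and a true difference is attenuated, for example from 5.8 to 5.8 × 0.9 = 5.2 points at 10% missing and 50% sustained. The rule is also sensitive to unequal missingness, which is why the observed-case result belongs with it.

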#### **8.2.3. Time to Pain Relief and Pain Freedom Postdose**

The following two secondary efficacy endpoints are captured in the subject eDiary separately from the scheduled time points, and are self-initiated based on the actual time of a subject's perception of pain relief and pain freedom (if they occur) within the first 2 hours postdose. Descriptive statistics for the two endpoints will be provided by treatment group for the FAS1 and FAS2. Additionally, the two endpoints will be summarized and graphically presented by treatment group for the FAS1 and FAS2 using Kaplan-Meier survival estimation. Comparisons between treatment groups will be performed using the log-rank test.

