##### **8.2.3.1. Time to Meaningful Headache Pain Relief Postdose**

Time to meaningful headache pain relief is defined as the time in minutes from the time a subject takes study drug until the time a subject indicates meaningful pain relief in the eDiary within 2 hours postdose. The time to meaningful headache pain relief postdose will be summarized and analyzed using Kaplan-Meier survival estimation for the FAS1 and FAS2. The corresponding p-values from a log-rank test will be computed for the comparison between treatment groups.

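### SAP 8.2 drops subjects from the 15-minute to 1.5-hour secondary analyses, and possibly from the 0-2 hour time-to-event analyses, because of rescue taken later; the size is unknown and probably small

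*SAP*

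**What the plan says.** SAP 8.2 sets one exclusion for the secondary endpoint analyses in FAS1 and FAS2. They "will exclude subjects who took rescue medication prior to the data collection" for the 2-hour assessment, and that cut-off carries a bracketed qualifier: "hours postdose time point (inclusive; LOCF", where the bracket closes. The rule acts on subjects, not on ratings, and its cut-off does not move with the time point being analysed.

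The endpoints under this rule include several measured before 2 hours:
- SAP 8.2.2 covers freedom from each of the three symptoms, from 15 minutes up to 24 hours.
- SAP 8.2.4 covers pain relief: "The proportion of subjects who have pain relief at 15, 30, and 45 minutes and 1, 1.5, 2, 4, and 24 hours postdose".
- SAP 8.2.5 and 8.2.6 use the same early time points for pain freedom and for absence of the Screening MBS.
- SAP 8.2.3 covers two time-to-event endpoints over the first 2 hours. One runs "until the time a subject indicates meaningful pain relief in the eDiary within 2 hours postdose", and for both "Comparisons between treatment groups will be performed using the log-rank test".

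None of these sections exempts ratings made before the rescue, and none gives a censoring rule at rescue. SAP 8.2.2 adds a condition on who is analysed: "Subjects who report a symptom predose and report the status of the symptom at the particular postdose time point will be analyzed". That condition concerns missing ratings and does not lift the rescue exclusion.

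Two other places bear on the point. Protocol 8.5.2 permits rescue only from 2 hours after dosing and after the 2-hour diary entry. SAP 9.2 defines rescue as medication taken 2 to 24 hours after study drug.

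**The concern.** Take a subject who takes other migraine medication 110 minutes after dosing. The ratings at 15, 30, 45, 60 and 90 minutes were all made before that intake and cannot have been affected by it. The rule nevertheless removes the subject from all five analyses. If it also covers the time-to-event endpoints, 110 minutes of observed follow-up are lost as well. Whether a subject belongs to the 15-minute analysis is thus decided by something that happens up to 2 hours later, after randomization, and that may depend on treatment.

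At stake is the comparison of randomized groups at the time points that describe onset of effect. If subjects who rescue early are mostly those not responding, deleting them raises the response rate in each arm. The difference between arms then moves unless the two effects happen to cancel.

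The rule also departs from the protocol without being declared for these endpoints. Protocol 10.5.1 bases secondary efficacy on the FAS, with no rescue exclusion. SAP 11, which lists departures from the protocol, records this exclusion only for the co-primary analysis. SAP 8.1.2 offers sensitivity analyses only for missing 2-hour co-primary data, so no planned secondary analysis brings the excluded subjects back.

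**Working it through.** **Anchor.** The documents give no early-rescue rate and no assumed response rate before 2 hours, so there is no plan figure for this point itself. The number per arm comes from Protocol 10.7: 600 × 0.85 / 2 = 255. As a check on that reading, take the first co-primary rates of 17.6% and 29.2% with two-sided 0.05. The null standard error is √(2 × 0.234 × 0.766 / 255) = 0.0375. The alternative standard error is √((0.176 × 0.824 + 0.292 × 0.708) / 255) = 0.0371. Then z = (0.116 − 1.96 × 0.0375) / 0.0371 ≈ 1.14, and power is 87.4% against the stated 88%. So 255 per arm is a fair stand-in for the analysed set.

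**Formula.** Let p be the response rate in an arm with everyone kept, and e the share excluded for early rescue. If those excluded are non-responders, the analysed rate is p / (1 − e).

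**Assumptions.** True 1-hour pain relief is 30% on placebo and 40% on DFN-15, a difference of 10.0 points. The early-rescue shares are a range, not estimates.

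| Early rescue, placebo/DFN-15 | Excluded of 510 | Placebo | DFN-15 | Difference (points) |
|---|---|---|---|---|
| 0%/0% | 0 | 30.0% | 40.0% | 10.0 |
| 2%/1% | about 8 | 0.30/0.98 = 30.6% | 0.40/0.99 = 40.4% | 9.8 |
| 5%/2% | about 18 | 0.30/0.95 = 31.6% | 0.40/0.98 = 40.8% | 9.2 |
| 10%/5% | about 38 | 0.30/0.90 = 33.3% | 0.40/0.95 = 42.1% | 8.8 |
| 10%/10% | 51 | 0.30/0.90 = 33.3% | 0.40/0.90 = 44.4% | 11.1 |
| 5%/10% | about 38 | 0.30/0.95 = 31.6% | 0.40/0.90 = 44.4% | 12.9 |

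The excluded counts are 255 times the two shares, added; for 5%/2%, 12.75 + 5.1 = 17.85.

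**No early effect.** With a true 10% rate in both arms, the rule alone creates a difference (DFN-15 minus placebo):
- 5%/2%: 0.10/0.98 − 0.10/0.95 = −0.3 points.
- 10%/5%: 0.10/0.95 − 0.10/0.90 = −0.6 points.
- 10%/2%: 0.10/0.98 − 0.10/0.90 = −0.9 points.

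**Limits of the arithmetic.** Not every excluded subject has five pre-rescue ratings: someone who rescues at 40 minutes has only those at 15 and 30 minutes. At 1 hour that person's rescue is already past, so the objection there is to deleting the subject rather than counting a non-response. No effect on the Kaplan-Meier curves or log-rank tests was calculated.

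**The SAP 9.2 definition.** If rescue means only medication at 2 to 24 hours, the rule catches subjects who took it at or after 2 hours but no later than a late 2-hour entry. For them every early rating and the whole 0-2 hour window precede the rescue, so everything discarded before 2 hours was valid.

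**The case against.** The strongest reply is that the rule touches very few people. Protocol 8.5.2 bars rescue before the 2-hour entry, so those excluded are deviators. At 2%/1% the difference moves by only 0.2 points. These are also secondary endpoints: SAP 8.1.1 makes trial success depend on the co-primaries alone, and the secondary tests have no hierarchy or multiplicity control. All of this stands and limits the weight of the point. It does not make the rule sound, because no analysis in the plan would show whether early rescue was in fact rare and balanced.

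A second reply is that the bracketed qualifier in "hours postdose time point (inclusive; LOCF" may confine the rule to LOCF analyses. SAP 8.2 specifies LOCF for secondary proportions, so the early proportions are covered either way. For the time-to-event endpoints the reply stands: the text leaves it unclear whether the rule applies. A reader might infer that early rescuers are certainly removed from the log-rank tests, but the documents do not settle that.

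A reader might also infer that deletion always raises the rate more in the arm with more rescue. It does not: at 5%/4% placebo rises from 30.0% to 31.6% (1.58 points) and DFN-15 from 40.0% to 41.7% (1.67 points). That early rescuers are non-responders is likewise an assumption; the documents contain no data on it.

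**Conclusion.** The point holds as a fault in a stated rule, not as a demonstrated distortion. As written, SAP 8.2 makes inclusion at 15 minutes to 1.5 hours depend on a later post-randomization event and discards valid ratings. Whether it does the same to the time-to-event analyses is unclear and needs to be stated.

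Under the assumptions above, a true 10.0-point difference is analysed as anything from 8.8 to 12.9 points across the shares shown. More early rescue on placebo works against DFN-15 in these examples; equal shares slightly enlarge the difference and leave the rate ratio unchanged; more early rescue on DFN-15 enlarges the difference. It is tempting to conclude that the onset-of-effect results will be materially biased. The documents do not support that, since they give no early-rescue rate and their own dosing rules imply that it should be low. The bias matters only if early rescue proves frequent or differs by arm.

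**What to change.** In SAP 8.2:
- Drop the subject-level rescue exclusion for the pre-2-hour time points and for both time-to-event endpoints, and keep all otherwise qualifying FAS1 and FAS2 subjects.
- Use every rating recorded before first rescue. Count pre-2-hour time points from rescue onward as non-response, neither deleted nor filled by LOCF.
- In the Kaplan-Meier and log-rank analyses, treat a subject who rescues without an event as event-free to 2 hours, with censoring at rescue as a check.
- Show the exclusion version only as a sensitivity analysis, and report the number excluded by arm.

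Reconcile the definition of rescue in SAP 9.2 with the rule in SAP 8.2, so that it is clear which intakes count, and clarify the LOCF qualifier. List in SAP 11 any departure from the protocol that remains for the secondary endpoints.

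The cost is SAP wording and a comparison of rescue time with rating time in the programs. SAP 3.3 already has the date and time of rescue recorded in the eDiary. One small burden remains: SAP 9.2 allows rescue to be reported outside the eDiary, so some times may be incomplete. SAP 6.3 imputes partial dates but not times, so a stated rule for incomplete rescue times is needed.
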